16.4.2 Data Collection and Follow-up for Withdrawn Subjects

We will make a strong effort (via phone calls and alternative contact information) to obtain follow-up information on all subjects who are prematurely withdrawn from the project.

Study Procedures

There are 3 main parts to this study. Depending on the subject's availability, the parts may be combined with visits for the Main Study. Thus, it is possible that one, two or all three of the MRI study visits (i.e., screening and the two MRI scan visits) will be combined with regular study visits.

16.5 Screening and Informed Consent (approximately 1.5 hours)

Upon arriving to the Informed Consent and Screening Visit, subjects will be asked to complete a breathalyzer test to ensure a breath alcohol concentration (BrAC) of 0.00 g%. Subjects will then undergo the informed consent process. Specifically, subjects will be provided a standard HIPAA form that contains privacy laws, and a study staff member will review the consent form with the

CONFIDENTIAL

This material is the property of the University of Pennsylvania. Do not disclose or use except as authorized in writing by the study sponsor

subject, including an explanation of the study protocol, its risks, potential benefits, and alternative treatment. Following resolution of any questions, subjects who appear to understand the nature of the study and consent will be asked to sign the study consent form. An entire copy of the informed consent form will be given to each subject. S/he is also reminded that the consent expresses willingness to participate but that the subsequent screening process will determine final eligibility. Further, s/he is reminded that participation is voluntary, and at any time, s/he may withdraw from the study.

Following consent, subjects will watch an fMRI video that simulates the experience of undergoing an MRI and meet with study staff to complete study assessments. They will also be asked to complete an MRI safety sheet. Baseline laboratory measures include: 1) urine drug screen (to determine the presence of psychoactive drugs); 2) electrocardiogram; 3) oral swab rapid HIV test (If the test is positive, study staff will draw a tablespoon of blood to conduct a confirmatory HIV blood test); and 4) for all females: a urine pregnancy test. In cases where blood samples are drawn and potential lab errors or abnormal findings occur, subjects will be asked to provide an additional blood sample to repeat the test(s).

Measures obtained (in addition to those obtained routinely for the Main Study):

a. Menstrual Cycle Questionnaire (MCQ) is a questionnaire administered by the Nursing Staff to all prospective female subjects that elicits information on menses status, menstrual cycle length, and premenstrual symptoms (PMS). This measure is acquired because hormone levels vary and cortical GABA levels decline from follicular to luteal phase of the menstrual cycle (Epperson, O'Malley et al. 2005), and these changes influence CBF (Krejza, Rudzinski et al. 2013) and behavior (Silveri, Sneider et al. 2013). Thus, this questionnaire (and progesterone/estrogen levels) will help us determine if females are pre-, peri- or post-menopausal.

b. Wechsler Abbreviated Scale of Intelligence (WASI) (Wechsler 1999) is a brief and reliable measure of intelligence that provides an estimate of an individual's IQ scores. We will use the two-subtest form (vocabulary and matrix reasoning) that offers an estimate of an individual's cognitive functioning. Individuals with an intelligence quotient of ≤ 80 are excluded because they do not have the cognitive skills necessary to participate in several of the study components.

All screening assessments will be performed to determine subject eligibility, and the results will be documented. The PI or study physician will confirm and sign off on the inclusion and exclusion criteria on a case report form prior to the subject being formally included in the study. Subjects will be called within 5 days of the screening visit to be informed of their eligibility for the sub-study. Eligible subjects will be booked for the Laboratory/MRI Scanning visit either before or on the day of the Main Study baseline visit based on their and the MRI scanner's availability. Subjects must complete MRI Scanning Visit 1 before starting to take the study medication.

c. CogState computerized battery is a 20-minute assessment of the cognitive effects of changes in drinking behavior and of topiramate treatment. A practice session of the CogState will be administered at the Screening and Informed Consent visit. Subsequent sessions of the CogState will be administered at the Laboratory/MRI session 1 and 2 visits. It consists of:

- Detection Task (Psychomotor Speed) [2 minutes]. For this test, subjects must press a response key as soon as they detect an event. The software measures the response time to detect each event.
- Identification Task (Attention) [3 minutes]. In this task an event occurs in the center of the computer screen and the subject must decide whether the event meets a predefined and unchanging criterion. The software measures the speed and accuracy of each response.

CONFIDENTIAL

- One Card Learning Task (Visual Learning) [5 minutes]. In this task a pre-determined set of six cards is shown repeatedly four times. Each time the set of six cards is presented the six cards are intermixed with eight distracter stimuli. Each distracter stimulus is shown only once in a task. Each time subjects see a stimulus presented in the center of the computer monitor they must decide whether they have seen this card in the task before. The software measures the speed and accuracy of each response.
- One Back Memory Task (Working Memory) [1 minute]: On this task the subject is shown a single stimulus in the centre of the computer screen (a card turns face up). They must decide whether the current card matches the card they had seen on the immediately previous trial. The software measures the speed and accuracy of each response.
- Shopping List Task (Verbal Learning and Memory) [5 minutes]: The test administrator reads the subject a brief list of words at the rate of one word every 2 seconds. After the list is complete, the subject is asked to recall as many of the words as possible. This process is repeated for a second and a third trial. After a delay, the subject is asked again to recall as many words as possible, without being read the list again. The total number of words recalled at initial recall and delayed recall are the outcome scores for this task.
- Groton Maze Learning Test (GMLT) (Reasoning and Problem Solving) [5 minutes]: The task begins with a chase task to familiarize the subject with the task context. The subject is shown a 10 x 10 grid of tiles on a computer touch screen and is instructed to “chase” a moving tile around the grid. This is followed by the timed chase test, where they must chase the target for 30 sec. The subject is then shown the same 10 x 10 grid of tiles on a computer touch screen. A 28-step pathway is hidden among the 100 possible locations, with the start and finish locations in the top left and bottom right of the grid, respectively. The subject is instructed to move one step from the start location and to continue, one tile at a time, toward the end. The subject moves by touching a tile next to the current location with the stylus. After each move, the computer indicates whether it is correct or incorrect. If a choice is incorrect, the subject must touch the last correct location and then make a different tile choice to advance toward the end. While moving through the hidden maze, the subject is required to adhere to two rules: no diagonal moves or touching the same tile twice in succession and no moving backwards along the pathway. The subject learns the 28-step pathway through the maze on the basis of this trial and error feedback. Once completed, the subject is returned to the start location and repeats the task, usually 4 more times, trying to remember the pathway just completed. There are 20 well-matched alternate forms for this task, and these are selected in pseudo-random order to ensure that no subject completes the same hidden path until all 20 have been completed. The software measures the total number of errors.

16.6 Laboratory/MRI Scanning Visit 1 (approximately 3 hours)

Upon arriving to the Laboratory/MRI Scanning visit, subjects will be asked to complete a breathalyzer test to ensure a breath alcohol concentration (BrAC) of 0.00 g%.

- Baseline laboratory measures include:
 - 1) urine drug screen (to determine the presence of psychoactive drugs);
 - 2) in all females: a urine pregnancy test and an additional blood sample for biochemical measurement of progesterone and estradiol levels to determine their menstrual cycle phase. A total of approximately 1 tablespoon of blood will be taken.

CONFIDENTIAL

In cases where blood samples are drawn and potential lab errors or abnormal findings occur, subjects will be asked to provide an additional blood sample to repeat the test(s).

Measures obtained (in addition to those obtained routinely for the Main Study):

a. CogState Computerized Battery: Described above.

b. Cognitive Bias Computer Tasks: Individuals with emotional or dependence disorders exhibit biased attention toward stimuli associated with their disorder. This bias appears to diminish following successful treatment. Several tasks will be administered: the dot-probe attention task, the primed attention task, the implicit association task, and a go/nogo inhibition task. Generally, subjects will be told that the purpose of the task is to see how quickly and accurately they can detect targets presented on a display terminal. During the tasks, the subject will be seated in front of an eye level computer screen. Alcohol, nonalcohol, pleasant and unpleasant pictures will be presented on the screen. Subjects will be given specific instructions for each task and will be asked to respond appropriately by pressing a button.

c. Within Session Rating Scale (WSRS): This scale is used to assess a person's desire to consume alcohol and their thoughts about the audio/visual images viewed during the scanning session.

Prior to the scan session, subjects will complete the CIWA-Ar and the AUQ to assess withdrawal symptoms and alcohol craving. Study staff will walk or take a taxi with the subject to the 3.0 Tesla scanner to complete the MRI scan. Prior to entering the scanner, subjects will be asked to drink to satiety to avoid potential confounding effects of thirst on neural responses to cues. During the scanning session, subjects will be asked to lie still with their eyes open for a 5 minute resting baseline scan, followed by two 10-minute audio-visual clips consisting of either alcohol-related cues: individuals differing in race, age and sex who are drinking alcohol and using explicit language designed to induce appetitive desire for alcohol; or non-alcohol-related cues that are similar in content, but individuals relate interesting short stories that do not portray alcohol consumption or alcohol reminders. Subjects will also be asked their level of alcohol craving (on a scale from 0-10) before and after each audio-video clip.

MRI scanning will be conducted on a Siemens 3.0 Tesla whole-body scanner (Siemens AG, Erlangen, Germany), using a standard Transmit/Receive head coil. A 30-second localizer scan and a 5-minute T1-weighted high-resolution scan are acquired before the functional scanning. These scans are used for subsequent normalization and anatomical co-registration of the images, and they provide subjects with a habituation period to the MRI environment. The 3-plane localizer scan (sagittal, axial and coronal) is acquired with FOV = 280 mm, TR/TE = 20/5ms, 192x144 matrix, and slice thickness 5mm. Acquisition parameters for the 3D High-Resolution MPRAGE structural in the axial plane are: FOV = 250 mm, TR/TE = 1620/3ms, 192x256 matrix, slice thickness 1 mm. The CASL technique will be used to acquire images during functional MRI (RB and SC exposure). Interleaved images with and without labeling will be acquired using a gradient echo echo-planar imaging sequence. A delay of 1000 ms will be inserted between the end of the labeling pulse and image acquisition to reduce transit artifact. Acquisition parameters are: FOV=22cm, matrix=64x64, TR/TE = 3000/17ms, flip angle=90°. Fourteen slices (8mm thickness with 1.5mm gap) will be acquired from inferior to superior in a sequential order. Each cue CASL scan with 200 acquisitions will be 10 minutes in length. The RB CASL scan will be 5 minutes with 100 acquisitions.

CONFIDENTIAL

16.7 Laboratory/MRI Scanning Visit 2 (approximately 3 hours)

After the subject has completed 6 weeks of medication in the main study, they will complete the second scanning session. Upon arriving at the TRC, subjects will be asked to complete a breathalyzer test to ensure a breath alcohol concentration (BrAC) of 0.00 g%. Procedures for the Laboratory/MRI Session 2 visit are identical to those for the first Laboratory/MRI Session.

17 Sub-Study Statistical Plan

17.1 Sample Size Determination

The current sample size is based on our previous research examining drug cue reactivity using audio-visual videos both on- and off-magnet through computerized tasks and during fMRI scanning.

17.2 Statistical Methods

17.2.1 Imaging Data Processing

Prior to performing analyses, brain data are examined for gross movement and full image acquisition. A Statistical Parametric Mapping (SPM)-based ASL data processing toolbox is used for data analyses. ASL image pairs are realigned to the mean of all control images and spatially smoothed with a 3D isotropic Gaussian kernel with full width at half maximum of 10mm. CBF image series are generated using a simplified two-compartment model with the sinc interpolation method for CBF calculations. The mean control image of each subject's data is co-registered to a high-resolution 3D T1 structural image using the mutual information based co-registration algorithm provided by SPM8. The same co-registration parameters are used to co-register the CBF maps to the structural image. The structural image is then spatially normalized to the Montreal Neurological Institute (MNI) standard brain. The same parameters are used to normalize the CBF images to the MNI standard space. Each subject's normalized mean control images are segmented using SPM8. The segmented gray matter masks are averaged and the overlap of subject's gray matter is extracted. This final mask is used for calculating global CBF for each session.

17.2.2 Imaging Data Analyses

Global CBF time course will be included in the model as a covariate to examine the effects of topiramate on regional CBF. No temporal smoothing will be applied. Contrasts between conditions (alcohol cue vs non-alcohol cue; scan 1 vs scan 2) will be defined in the general linear model to assess the voxel by voxel CBF difference. Using the corresponding parametric maps of this contrast (β maps), random effects analysis will be employed to test for a significant main effect of condition with a statistical parametric map of the T statistic at each voxel for population inference for each session for the placebo and topiramate groups (second-level analysis). A 2x2 factorial design matrix will be used to assess the effects of the pharmacological manipulation by including the group (topiramate vs placebo) and condition (scan 1 vs scan 2) as the two factors. An associated contrast will be defined in this model to examine administration effects. This two-stage analysis is theoretically equivalent to a 2-way analysis of variance (ANOVA). Simple regression analyses will be conducted on CBF with the change in craving scores [post-alcohol cue minus pre-alcohol cue craving scores, number of heavy drinking days during the past 30 days, and age] as covariates of interest to test for prognostic brain/behavioral correlations. For the exploratory aim, subjects will be grouped by genotype (CC vs A-allele carrier) to examine the moderating effects of rs2832407 in *GRIK1* on topiramate effects using the same simple regression analyses described above. We will limit this analysis to European

CONFIDENTIAL

Americans, as that is the population in which the preliminary findings were obtained and allele frequencies differ significantly by population.

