5.3 Method for Assigning Subjects to Treatment Groups

Subjects will be randomly assigned to one of two treatment conditions using a block randomization scheme: topiramate 200 mg/day (n = 100) or placebo (n = 100). A designated randomization staff member who is not otherwise involved in the conduct of the study will work with the Investigational Drug Service (IDS) staff to implement the randomization. The process for randomization is: 1) a study coordinator will complete a “block randomization form,” which includes the variables to be entered into the block randomization program [i.e., sex, genotype (i.e., C-allele homozygote vs A-allele carrier), number of heavy drinking days in the past month (trichotomized)]; 2) the randomization staff member will enter the variables into the block randomization program; 3) the randomization staff member will fax the randomization group to IDS, who will assign a kit number to subject and fax kit assignment to research coordinator; 4) the research nurse or physician will dispense medication to the subject and complete and sign the IDS prescription form included in the starter kit; 5) the research coordinator will fax the completed form to IDS.

Study drug for subsequent visits will be ordered by the research coordinator using the “Research Pharmacy Schedule” form (following the schedule in Table 1), a copy of which will be retained in the subject’s research file. At each visit, the research nurse will dispense a supply of study medication. In the event that scheduled visits change or the subject’s dosage is adjusted by the study physician, medication will be mailed via a UPS or Fedex to the subject, to ensure that they have enough medication to get them to their next scheduled visit. The study physician will approve all medication mailed to subjects and the study nurse or physician will document the medication dispensed via mail and call to ensure and instruct the patient on how the medication should be taken and to document all AEs. Study staff will also document whether the mailed medication was received by the subject.

Subjects with severe psychological symptoms or determined to be inappropriate for the study by an investigator will be withdrawn from the study. Subjects who are withdrawn completely will be referred for appropriate clinical care.

CONFIDENTIAL

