15.1 General Design

- **Phase II Study** - This is a phase 2 research study aimed at identifying the brain and behavioral mechanisms underlying the GABA/glutamate modulator, topiramate.
- **Design** – One hundred heavy drinkers who meet DSM-5 criteria for AUD and express an interest in reducing or stopping drinking will be recruited from the main study, screened, consented, and if eligible, receive 2 MRI scans. Scan 1 will occur before Topiramate or placebo is administered in the main study. Scan 2 will occur after subjects have received at least six weeks of medication in the main study (i.e., 6-8 weeks from the first dose of study medication). We will use perfusion and blood oxygen-level dependent (BOLD) fMRI during resting state and alcohol cue exposure to acquire brain and behavioral responses when the brain is “at rest” and during exposure to alcohol cues. The goals of this study are to pilot test the validity of our alcohol cues and to identify brain and behavioral mechanisms of topiramate in reducing heavy drinking in alcohol dependent individuals.

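### The imaging sub-study's group-by-scan model names no subject term and no treatment contrast, so followed literally it gives the topiramate test the wrong error term

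*Combined protocol and SAP*

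**What the plan says.** Section 15.1 sets out a paired design. It plans for "One hundred heavy drinkers who meet DSM-5 criteria for AUD" who are to be "screened, consented, and if eligible, receive 2 MRI scans", the first before any study medication and the second 6 to 8 weeks after the first dose.

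Section 17.2.2 builds the test of the drug from a 2x2 factorial design matrix, "by including the group (topiramate vs placebo) and condition (scan 1 vs scan 2) as the two factors". The treatment test itself is described only as follows: "An associated contrast will be defined in this model to examine administration effects". The model is then characterised: "This two-stage analysis is theoretically equivalent to a 2-way analysis of variance (ANOVA".

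Earlier in the same section, "Contrasts between conditions (alcohol cue vs non-alcohol cue; scan 1 vs scan 2) will be defined in the general linear model". A random-effects analysis follows, but it is tied to the main effect of condition for each session within each arm. For the 2x2 model, the section names no subject factor, repeated-measures term, covariance structure or change score.

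**The concern.** Scan 1 and scan 2 come from the same person, so stable differences between people in cerebral blood flow appear in both. A two-way ANOVA on group and scan alone has a single residual, and that residual contains those stable differences. The paired design exists to remove them.

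Hypothesis 1 (Section 14) predicts that topiramate dampens activity while placebo activity does not change from before to after treatment. That is a difference in change between arms, that is, the group x scan contrast. With the wrong residual, this contrast is tested against too large an error and a real effect is more likely to be missed. Section 17.1 gives no effect size, standard deviation or power for the sub-study, so no margin is shown that could absorb the loss.

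The unnamed contrast adds a second problem. If the analyst took the group main effect instead, the same omission would push the error in the opposite direction.

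**Working it through.** The sub-study states no power or standard error, so there is no figure of the plan's own to reproduce. The check is analytic.

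**Inputs**
- Two scans per person (Section 15.1).
- n = 50 per arm: 100 participants (Section 15.1), assuming that the main study's equal allocation carries over (Section 5.3: "topiramate 200 mg/day (n = 100) or placebo (n = 100").
- Common SD s at both scans, set to 1.
- Correlation rho between a person's two scans: not given for cerebral blood flow. The 0.35 in Section 7.1 belongs to the heavy-drinking outcome. Values of 0.3, 0.5 and 0.7 are assumed.
- Two-sided alpha 0.05. Section 17.2.3 gives .05 for the behavioural analyses; two-sided testing is assumed.

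**Group x scan contrast** (difference between arms in mean change)
- Variance of one person's change: 2(1-rho)s².
- True SE: sqrt(4(1-rho)s²/n).
- SE from the two-factor model with independent errors: sqrt(4s²/n) = sqrt(4/50) = 0.283.
- Ratio: 1/sqrt(1-rho).

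The omission inflates only the estimated SE; the real sampling spread of the contrast does not change. So the ratio multiplies the critical value. For an effect that has 80% power with pairing (1.96 + 0.84 = 2.80 true SEs), power is Phi(2.80 - 1.96 x ratio). The actual type I error is 2(1 - Phi(1.96 x ratio)).

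| rho | True SE | Model SE | Ratio | 2.80 - 1.96 x ratio | Power | Actual type I error |
|---|---|---|---|---|---|---|
| 0.3 | 0.237 | 0.283 | 1.20 | 0.46 | 68% | 1.9% |
| 0.5 | 0.200 | 0.283 | 1.41 | 0.03 | 51% | 0.6% |
| 0.7 | 0.155 | 0.283 | 1.83 | -0.78 | 22% | 0.03% |

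At rho = 0 there is no distortion. At negative rho the direction reverses.

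**Group main effect** (mean of both scans)
- True SE: sqrt((1+rho)s²/n). Model SE: sqrt(s²/n). Ratio: 1/sqrt(1+rho).
- Ratios are 0.86, 0.82 and 0.77 at rho 0.35, 0.5 and 0.7.
- Type I error, 2(1 - Phi(1.96 x ratio)), is about 9%, 11% and 13%.

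**Check by simulation** (50 per arm, 20,000 data sets per value of rho). At rho 0.35, 0.5 and 0.7 the SE ratios for group x scan were 1.24, 1.42 and 1.83. Type I error for the group main effect was 8.9%, 10.9% and 13.6%. The change-score comparison held its type I error at 5.0%, 5.0% and 4.9%.

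**The case against.** The strongest reply is that the section never says that the two scans are independent. Two factors and a two-way ANOVA label describe fixed effects, and a two-way ANOVA can have a repeated factor. The section also lists scan 1 versus scan 2 among the general linear model contrasts and mentions random effects and two stages, so a within-person analysis may be intended.

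Part of this stands. A reader might infer that the plan declares the scans independent; it does not. Independence follows only from fitting the named model literally. The other wording does not settle the matter, however. The random-effects sentence works within each session and arm, so it does not link a person's two scans. And if per-person scan differences had already been taken, scan could not remain a factor in the 2x2 model. For comparison, Section 7.2 does name a random intercept for the main study's repeated measures.

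A reader might also infer that the treatment-effect error bars are simply too wide. That holds only for the group x scan contrast and only with positively correlated scans. Hypothesis 1 points to that contrast, but Section 17.2.2 does not name it, and for a group main effect the bars would be too narrow.

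It is also fair to say that the sub-study is optional and partly a pilot of the alcohol cues, and that for group x scan the error is conservative: it could hide an effect but would not create a false one.

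**Conclusion.** The point holds in conditional form. As written, Section 17.2.2 specifies a model for paired scans without saying how the pairs are linked or which contrast is the treatment effect. Fitted literally, it gives a wrong error term for either candidate contrast unless the scans are uncorrelated. For group x scan, the loss runs from 80% power to about 68% at rho 0.3 and about 22% at rho 0.7. For a group main effect, type I error would be about 9 to 13% at rho 0.35 to 0.7.

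The sizes rest on the assumed rho, on equal variance at the two scans and on about 50 people per arm, although the SE ratios do not depend on the number per arm. The documents do not support extending the concern to the trial's primary heavy-drinking analysis. The wording should be corrected before the imaging data are analysed.

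**What to change.** In Section 17.2.2:
- Name group x scan as the treatment contrast, in line with Hypothesis 1.
- Test it by computing each subject's scan 2 minus scan 1 map, once for cue minus non-cue and once for the resting scan, and comparing the arms with a two-sample test. Alternatively, keep the factorial and add a subject factor or a modelled within-subject covariance.
- Replace the sentence that equates the analysis with a two-way ANOVA.

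The cost is a change of wording in the sub-study analysis, with no new data or procedures. The downside is that subjects with only one scan drop out of the paired contrast, so their number in each arm should be reported.

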13.2 Risk/Benefits

Potential Risks

The potential risks of this study include the small risk incurred by venipuncture

Potential Benefits

Subjects will receive close psychiatric and medical attention, including careful evaluation of their medical and psychiatric status. The potential benefits to society include a potential improvement in the effectiveness of treatment for problem drinking, which may reduce the personal and societal costs associated with the problem.

Risk Benefit Ratio

The potential benefits of this study far outweigh the potential risks. Alcohol use disorders are serious disorders with mildly effective pharmacotherapy. Even in the best programs, relapse rates are high. Individuals accepted into this study will receive close medical and psychiatric monitoring. Subjects will be screened prior to admission into the study and those at risk for adverse reactions will be excluded.

14 Sub-Study Objectives

Objective 1: Demonstrate neuromodulatory effects of a GABA/glutamate modulator, topiramate, on RB and alcohol cue reactivity

CONFIDENTIAL

This material is the property of the University of Pennsylvania. Do not disclose or use except as authorized in writing by the study sponsor

Hypothesis 1: We hypothesize that topiramate will ameliorate neurophysiological vulnerabilities by dampening neural activity in the brain ‘at rest’ *and* during alcohol cue exposure in reward-related regions, such as the amygdala, mOFC, VS, and the insula. In contrast, neural activity in placebo-treated individuals at rest and in alcohol cue reactivity will not differ from pre- to post-treatment.

Objective 2: Examine the mechanism underlying topiramate’s ability to blunt alcohol cue reactivity and reduce heavy drinking days

Hypothesis 2: We hypothesize that there will be a direct relationship between RB in the VS and mOFC and its effects on alcohol cue reactivity. Although overall effects are expected, reductions in heavy drinking days will correlate with topiramate’s ability to modulate reward circuitry responses.

Exploratory Objective: Examine the moderating effects of rs2832407 on topiramate’s effects on brain and behavioral responses

Exploratory hypothesis: C-allele homozygotes at this locus will show the most robust effects of topiramate.

15 Sub-Study Design

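### The sub-study's brain-behaviour regression uses a 30-day level of heavy drinking days, so neither part of Hypothesis 2 has a matching analysis

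*Combined protocol and SAP*

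**What the plan says.** Section 14 gives the sub-study two numbered objectives and labels only the genotype question exploratory. Objective 2 asks how topiramate comes to "blunt alcohol cue reactivity and reduce heavy drinking days". Hypothesis 2 has two parts. The first is that "there will be a direct relationship between RB in the VS and mOFC and its effects on alcohol cue reactivity". The second is that "reductions in heavy drinking days will correlate with" the drug's capacity to alter reward-circuit responses.

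Section 17.2.2 contains one analysis that joins brain and behaviour: "Simple regression analyses will be conducted on CBF with the change in craving scores". Craving change is defined within a scanning session, as "post-alcohol cue minus pre-alcohol cue craving scores". The same bracket then lists "number of heavy drinking days during the past 30 days" and age. All are entered "as covariates of interest to test for prognostic brain/behavioral correlations".

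Earlier in the same section, "Contrasts between conditions (alcohol cue vs non-alcohol cue; scan 1 vs scan 2) will be defined in the general linear model", and a group-by-scan factorial model assesses the drug effect. Neither names a drinking variable.

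Section 17.2.3 makes factor scores covariates for the imaging data but defines no change in drinking. Section 15.1 plans 100 subjects with two scans each, the second 6 to 8 weeks after first dose. Section 17.1 bases the sample size on previous research and states no effect size, SD or power.

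**The concern.** The drinking part of Hypothesis 2 relates a change to a change: how much heavy drinking fell against how much the brain response moved under treatment. The regression relates an unspecified CBF measure to how heavily a person drank over some 30-day period. A correlation with drinking severity could then be reported as evidence of mechanism.

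The regression as listed also has no medication term, so it cannot separate modulation by topiramate from differences between drinkers that exist in either arm. If the scan, drinking window and region are chosen after the data are seen, the analysis is open to selective reporting.

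**Working it through.** **1. Hypothesis against analysis**

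| Element | Hypothesis 2 (section 14) | Regression in 17.2.2 |
|---|---|---|
| Drinking variable | Reduction in heavy drinking days (HDD) | HDD level over 30 days |
| Anchor | Before against during treatment | Not stated |
| Brain variable | Modulation by topiramate | CBF, map not stated |
| Medication | Central | Not among the listed terms |
| Baseline drinking | Implied by a reduction | No adjustment listed |
| Resting CBF against cue reactivity | First part of the hypothesis | No model listed |

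**2. What the 30 days would cover**

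Anchored at scan 1, the window is wholly pre-treatment. For scan 2, count day 1 as first dose and let the window end on the scan day. A scan on day 42 covers days 13 to 42; a scan on day 56 covers days 27 to 56. Table 1 (section 5.2) reaches the maximum dose in week 6, that is from day 36. So 23 of the 30 days (13 to 35) precede it in the first case and 9 of 30 (27 to 35) in the second. The main trial's primary contrast uses weeks 7 to 12 (sections 7.1 and 7.2).

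**3. How well a level stands in for a reduction (illustration only)**

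There is no figure in the plan to reproduce. Let X1 and X2 be HDD before and on treatment, rho their correlation, and k the ratio SD(X2)/SD(X1). The reduction is X1 − X2.

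- corr(X1, reduction) = (1 − rho·k) / sqrt(1 + k² − 2·rho·k)
- corr(X2, reduction) = (rho − k) / sqrt(1 + k² − 2·rho·k)

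With k = 1 these become +sqrt((1 − rho)/2) and −sqrt((1 − rho)/2). The sign therefore depends on the anchor that the plan leaves open.

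Now assume a true correlation of 0.30 between CBF change and HDD reduction, and that CBF change relates to the level only through the reduction. Approximate power by Fisher z at two-sided 0.05, with n = 100. For the change score: atanh(0.30) × sqrt(97) = 3.05, and 3.05 − 1.96 = 1.09, which gives 86%. For the level at rho = 0.5: 0.30 × 0.50 = 0.15; atanh(0.15) × sqrt(97) = 1.49, which gives 32%.

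| rho (k = 1) | Absolute correlation of level with reduction | Power using level |
|---|---|---|
| 0.2 | 0.63 | 47% |
| 0.35 | 0.57 | 40% |
| 0.5 | 0.50 | 32% |
| 0.7 | 0.39 | 21% |

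The 0.35 is the main trial's assumed within-subject correlation (section 7.1). It belongs to repeated measures over weeks 7 to 12, not to 30-day totals.

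**4. Sensitivity to unequal SDs**

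Entry requires at least 2 HDD per week (section 4.1), which restricts the spread at baseline but not later, so k need not be 1. Take rho = 0.5, n = 100 and the same assumed 0.30:

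| k | Scan 1 level: correlation, power | Scan 2 level: correlation, power |
|---|---|---|
| 1.5 | 0.19, about 9% | −0.76, about 62% |
| 0.75 | 0.69, about 55% | −0.28, about 13% |

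No single figure describes the loss.

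**The case against.** **CBF change is planned.** A reader might infer that the sub-study has no analysis of change in blood flow. The documents do not support that: section 17.2.2 defines scan 1 versus scan 2 contrasts and carries contrast maps to the second level. Those maps may have been the intended regression outcome, but the text does not say so. Even on that reading the drinking variable remains a level.

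**The regression is called prognostic.** It does not claim to test Hypothesis 2, and past-30-day HDD is a reasonable covariate for a prognostic correlation. This stands. The regression is not invalid for its stated purpose; the hypothesis simply has no analysis assigned to it.

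**Change might govern the whole bracket.** Age sits in the same bracket and only craving has a post-minus-pre definition, so the wording does not support reading HDD as a change score.

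**A level can be enough.** With baseline HDD in the model, regressing follow-up HDD on CBF change gives the same CBF coefficient, apart from sign, as regressing the reduction. This is correct. The essential gaps are the missing baseline adjustment, anchor, CBF definition and medication term, rather than the word level in itself.

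**The power figures.** A reader might infer that following the plan cuts power from 86% to 32%. The documents give no basis for rho, equal SDs or a true correlation of 0.30. A Fisher z test of one correlation is also not the planned voxel-wise analysis, and 100 is the number recruited, before any missed second scans.

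**Conclusion.** The concern holds as a mismatch between hypothesis and analysis. Followed literally, section 17.2.2 tests neither the drinking part of Hypothesis 2 nor the part relating resting CBF to cue reactivity. This rests on the text alone and does not depend on the illustration.

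The size of the loss is not determined by the documents. The range of 0.39 to 0.63 for level against reduction assumes equal SDs and rho from 0.2 to 0.7, and unequal SDs widen it considerably.

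The matter should be corrected because it affects a numbered, non-exploratory objective. That objective belongs to an optional sub-study, and the main trial's primary analysis and safety monitoring are unaffected.

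**What to change.** Amend section 17.2.2 as follows.

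- **HDD part.** Regress Timeline Follow-back (TLFB) HDD in one prespecified on-treatment window on scan 2 minus scan 1 CBF in the ventral striatum (VS) and medial orbitofrontal cortex (mOFC), at rest and for the cue contrast. Adjust for HDD in the 30 days before scan 1 and for medication group. Weeks 7 to 12 would match the main trial. Express HDD as a rate, since 30 and 42 days differ in length, and note that scan 2 falls at or near the start of that window.
- **Medication by CBF change.** Report this term as a secondary estimate. It will be imprecise with at most 100 subjects. If the arms are about equal, roughly 50 received topiramate, and the illustration above gives 56% power for a correlation of 0.30 at n = 50.
- **Resting-CBF part.** Add a regression of cue reactivity on resting CBF in the VS and mOFC.
- **Multiplicity.** Two regions and two CBF measures give four coefficients for the HDD part. State which leads, or how they are adjusted.
- **Existing regression.** Keep it as prognostic only, and name the CBF map and the scan that anchors the 30 days.

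The cost is wording and slightly more analysis. TLFB covers 90 days at intake and is repeated at each treatment visit (section 6.2), and both scans are already planned, so no new data are needed. The change should be made before unblinding.
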